### 5.2. Determination of Sample Size

Based on the Disease Progression Model (DPM), 360 enrolled patients, a 30% dropout rate, and a 3-month delay of treatment effect onset, this sample size will provide more than 95% power to

demonstrate that at least one of the active treatment arms has slowed cognitive/functional decline. This claim of slowing cognitive/functional decline is based on showing that at least one of the active treatment arms has a  $\geq 0.6$  posterior probability of slowing of iADRS progression over placebo by at least 4 points (that is, 25% slowing relative to placebo, based on a mean change from baseline in the placebo group of 16 points and mean change from baseline on at least one of the active treatment arms of at most 12 points) after 104 weeks (approximately 24 months) on study treatment. This power calculation comes from simulations using a placebo decline of 19.56 points and 33% slowing on 1400 mg LY3303560 and 50% slowing on 5600 mg LY3303560 relative to placebo at 104 weeks. The variance-covariance matrix in the simulations had a variance at Week 104 of 436.85 (equal to a standard deviation of 20.9). If both active treatment arms are placebo-like with no efficacy, the probability of passing the efficacy criterion specified above (that is, false positive) is approximately 2.5%. To test the hypothesis of a disease progression benefit, we calculate the posterior probability of superiority in cognitive/functional slowing, and if it is above a pre-specified threshold (which controls the experiment-wise type I error at approximately 2.5%), then a claim of cognitive slowing will be made. The simulation for the power calculation and sample size determination was carried out in FACTS Version 5.5.

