### 6.3.2. *Handling Missing Items in Calculating Totals*

If any of the individual items for ADAS-Cog or ADCS-ADL are missing or unknown, every effort will be made to obtain the score for the missing item or items.

For ADAS-Cog13, if fewer than 4 of a total of 13 items are missing, the total score (maximum =85) will be imputed as follows: the total from the remaining items will be multiplied by a factor that includes the maximum score for the missing items. For example, if the first item, "Word-Recall Task," which ranges from a score of 0 through 10 (maximum = 10), is missing, and the second item "Commands," which ranges from a score of 0 to 5 (maximum = 5), is missing, then the multiplication factor =  $85/(85 - [10 + 5]) = 85/70 = 1.21$ . Thus, the total score for this example will be the sum of the remaining 11 items multiplied by 1.21. The

imputed number will be rounded up to the nearest integer. If more than 4 items are missing, the total score for ADAS-Cog13 at that visit will be considered missing.

For the ADCS-iADL, if <30% of the items are missing, the total score will be imputed (maximum = 59). The sum of the nonmissing items will be prorated to the sum of total items. The imputed number will be rounded up to the nearest integer. If the nearest integer is greater than the maximum possible score, the imputed score will be equal to the maximum score. If >30% of the items are missing, the total score for ADCS-iADL at that visit will be considered missing. The same imputation technique will be applied to the ADCS-ADL total score. Note that, depending on the specific item responses that are missing, it is possible to have an imputed total score for both the ADCS-iADL and the ADCS-ADL, an imputed total score for one but not the other, or both total scores missing.

The same imputation technique will be applied to the CDR-SB. If only 1 box (of 6) of the CDR is missing, the sum of the boxes will be imputed by prorating the sum from the other 5 boxes. If the score from more than 1 box is not available, the CDR-SB at that visit will be considered missing.

The iADRS score is calculated as follows:  $iADRS \text{ score} = [-1(ADAS - Cog_{13}) + 85] + ADCS-iADL$  (Wessels et al. 2015). If either ADAS-Cog13 or ADCS-iADL is missing, iADRS score will be considered missing.

For all other scales, if any item is missing, any total or sum involving that item will be considered missing.

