### 6.11.3.4. Delta Adjustment Tipping Point Analysis

Sensitivity to departures from the missing-at-random (MAR) assumption will be investigated using a tipping point analysis (Carpenter and Kenward 2013). This method is a sensitivity analysis in multiple imputation under the missing-not-at-random (MNAR) assumption that searches for a tipping point that reverses the study conclusion. Departures from MAR in the LY3303560 treatment groups will be assessed assuming that patients who discontinue the study have, on average, efficacy outcomes after discontinuation that are worse by some amount  $\delta$  compared to other similar patients with observed data (ie, compared to a value which would have been assumed under an MAR model). A series of analyses will be performed with increasing values of  $\delta$  until the analysis conclusion of a statistically significant treatment effect no longer holds. The value of  $\delta$  that overturns the primary results will represent a tipping point. An interpretation of clinical plausibility of the assumption underlying the tipping point will be provided.

Mean changes from baseline in iADRS scores will be analyzed based on data observed while the patient remains on study as well as data imputed using multiple imputation (MI) methodology for time points at which no value is observed. Imputed values in the LY3303560 treatment groups will first be sampled from an MAR-based multiple imputation model and then  $\delta$ -adjusted as described below.

Missing-at-random-based imputations will be generated for iADRS scores at each time point, and then a value of  $\delta = \{\Delta\}$  will be added to all imputed values in the LY3303560 treatment groups prior to analyzing multiply imputed data. This approach assumes that the marginal mean of imputed patient measurements is worse by  $\delta$  at each time point after discontinuation compared to the marginal mean of patients with observed data at the same time point. Analyses will be conducted with values of  $\delta$  starting from 0 with increments of 0.10 until the null hypothesis can no longer be rejected.

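### The tipping-point analysis adds a non-negative delta to imputed iADRS scores, which improves active-arm dropouts instead of making them worse

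*SAP*

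**What the plan says.** Section 6.11.3.4 describes a delta-adjusted multiple imputation analysis of mean change from baseline in iADRS. Missing iADRS scores are first imputed under missing at random. For the LY3303560 arms, delta then "will be added to all imputed values in the LY3303560 treatment groups prior to analyzing multiply imputed data". The next sentence explains that the approach "assumes that the marginal mean of imputed patient measurements is worse by" delta at each time point after discontinuation, and an earlier sentence in the section says the same. The values of delta run "starting from 0 with increments of 0.10 until the null hypothesis can no longer be rejected". The section also says that the delta "that overturns the primary results will represent a tipping point".

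The direction of the scale comes from Section 6.3.2 ("The iADRS score is calculated as follows"): iADRS = (85 − ADAS-Cog13) + ADCS-iADL. Section 5.2 supplies the planning values: "360 enrolled patients, a 30% dropout rate", and "simulations using a placebo decline of 19.56 points and 33% slowing on 1400 mg LY3303560 and 50% slowing on 5600 mg LY3303560".

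**The concern.** The stated assumption and the stated operation point in opposite directions. If dropouts are to be worse by a non-negative delta on a scale where higher is better, delta must be taken away from the imputed scores. Programmed literally, the analysis makes active-arm dropouts progressively better than missing at random and leaves placebo dropouts unchanged.

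Section 6.3.1 relies on missing at random and Section 5.2 plans for 30% dropout. This is the only analysis the SAP names for departures from that assumption. Run as written, it would find no tipping point, and a reader could take that as unlimited robustness. The clinical-plausibility discussion that the section promises would have no value to discuss.

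**Working it through.** **Direction of the scale.** The ADAS-Cog13 maximum is 85 and the ADCS-iADL maximum is 59 (Section 6.3.2).
- ADAS-Cog13 = 0 and ADCS-iADL = 59: iADRS = 85 + 59 = 144.
- ADAS-Cog13 = 85 and ADCS-iADL = 0: iADRS = 0 + 0 = 0.
- One more ADAS-Cog13 point lowers iADRS by 1; one more ADCS-iADL point raises it by 1.

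Higher is therefore better. Adding delta to the score or to its change from baseline (post minus baseline) has the same effect.

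**Illustration.** Section 6.11.3.4 gives no tipping value to reproduce, so the size is shown with the planning values of Section 5.2 and the 1:1:1 allocation of Section 5.1.
- Per arm: 360/3 = 120; missing fraction p = 0.30; observed 0.70 × 120 = 84.
- Variance at Week 104: 436.85.
- Benefit: 0.33 × 19.56 = 6.45 points, or 0.50 × 19.56 = 9.78 points.

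With delta d added to the active arm's imputed values:
- difference = benefit + p·d
- variance = 2 × 436.85/84 + p(1 − p)d²/120 = 10.40 + 0.00175·d²
- z = difference/√variance, compared with 1.96

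SE is 3.225 at d = 0 and 3.252 at d = 10. A negative d in the table means that delta is subtracted.

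| d | z, 33% slowing | z, 50% slowing |
|---|---|---|
| −10 | 1.06 | 2.08 |
| −5 | 1.53 | 2.56 |
| 0 | 2.00 | 3.03 |
| +5 | 2.46 | 3.49 |
| +10 | 2.91 | 3.93 |

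For example, at d = +10 with 50% slowing: (9.78 + 3.00)/3.252 = 3.93. At d = −10: (9.78 − 3.00)/3.252 = 2.08.

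**Can the rule as written ever stop?** The p(1 − p)d² term inflates the variance, so the limit needs checking. As d grows, z tends to p/√(p(1 − p)/120) = √(120 × 0.30/0.70) = 7.17. Since z starts above 1.96 and the limit is far above it, z does not fall below its starting value. The limit would drop to 1.96 only if p/(1 − p) = 1.96²/120 = 0.032, that is, at about 3% missing, far from the planned 30%.

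**With delta subtracted.** Solving z = 1.96 gives d = 0.45 (33% slowing) and 11.30 (50% slowing). The first 0.10 steps at which significance is lost are 0.5 and 11.4. For 50% slowing the value is about 18.6 at 20% dropout and about 7.3 at 40%.

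**Simulation checks.** Direct multiple imputation (50 imputations, 1,500 trials, missing completely at random) gave mean z at d = −10, −5, 0, 5, 10 of 1.03, 1.50, 1.97, 2.43, 2.88 (33%) and 2.04, 2.51, 2.98, 3.44, 3.88 (50%), close to the formula. A separate simulation with 50% slowing searched the 0.10 grid up to 100. With delta added, 0 of 46 initially significant trials tipped. With delta subtracted, 50 of 50 tipped, at a median of 13.2 points.

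**The case against.** The strongest reply is that the intent is plain: the sentences around the instruction say the imputed outcomes are worse, and the search is meant to end when significance is lost. Only one verb points the wrong way. The analysis is exploratory, leaves the Bayesian disease progression model untouched, and would expose its own error because the loop would not stop. All of this is right, and it limits the weight of the point. It does not make the written algorithm correct.

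A second reply is that the SAP may count worsening as positive. Section 5.2 gives placebo and active changes as unsigned 16 and 12 points, and Section 6.11.1 centres the prior for the per-visit placebo change at +1.25. On such a convention, adding delta would worsen the outcome. But neither passage defines a reversed score, the prior is very diffuse and belongs to a different model, and Section 6.11.3.4 names iADRS scores as the quantity imputed. At best, a needed sign convention is never stated.

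A third reply, that the tipping values are fragile, stands. Using all 120 patients per arm in the standard error gives 14.6 and 3.9 in place of 11.4 and 0.5. The 84 observed patients are the better basis, because imputation adds no information and the multiple imputation simulation agrees with that standard error. The values remain illustrative. Finally, the remark about overturning the primary result is an editorial point and adds nothing to the severity.

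**Conclusion.** The concern holds. Section 6.11.3.4 tells the programmer to improve the imputed active-arm scores while assuming that they are worse. That follows from the iADRS formula and the non-negative grid, and needs no numerical assumption. At the planned 30% dropout, and from a result significant in favour of drug, the stopping rule is not reached: z moves from 2.00 or 3.03 towards 7.17.

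The tipping values with delta subtracted (0.5 and 11.4 points) rest on 360 patients, a Week 104 comparison alone, no borrowing from earlier visits and equal dropout across arms. Section 1 speaks of approximately 225 patients. With 75 per arm and 52.5 observed, SE = √(2 × 436.85/52.5) = 4.08, z for 50% slowing starts at 9.78/4.08 = 2.40 and the limit is √(75 × 0.30/0.70) = 5.67, so the conclusion is the same. For 33% slowing z would be 6.45/4.08 = 1.58, and no search would begin.

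This should be fixed, but it puts no confirmatory claim at risk. A secondary wording point also holds: the comparison being tipped is the multiply imputed mean-change analysis, not the primary disease progression model with its posterior-probability threshold.

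**What to change.** In Section 6.11.3.4, state that delta is subtracted from the imputed iADRS scores in the LY3303560 arms or, equivalently, that 0, −0.10, −0.20 and so on is added. Add that a higher iADRS score is better, so that the sign can be checked from the section itself. Reword the tipping-point sentence to say that the tipping point is the delta at which the multiply imputed mean-change comparison is no longer statistically significant.

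The cost is small wording changes in one section and one sign in the program. No new data or additional analysis is needed.

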#### **6.16.2. Safety Summaries for Interim Analysis 2**

The efficacy analyses used in Interim Analysis 2 (IA2) will be detailed in the Interim Efficacy SAP. In addition to the listings and summaries reviewed at IA1, the following analyses will be included in Interim Analysis 2 (IA2):

- Listing of patients missing site assessments and infusions because of COVID-19
- Listing of patients discontinuing the study because of COVID-19
- Dot plot of visits (x-axis) by patient (y-axis) with color denoting missed infusions
- Summary of ADA
- ANCOVA of change in whole brain volume from vMRI

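### The tipping-point shift is justified for outcomes after discontinuation but is written to cover every imputed active-arm iADRS score, so the reported delta can be smaller than the dropout quantity it is meant to measure

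*SAP*

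**What the plan says.** SAP Section 6.11.3.4 describes scope in four places.

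- **Assumption.** The departure from MAR concerns the active arms and supposes that "patients who discontinue the study have, on average, efficacy outcomes after discontinuation that are worse by some amount" delta.
- **What is imputed.** The analysis uses observed data together with "data imputed using multiple imputation (MI) methodology for time points at which no value is observed".
- **What is shifted.** A value of delta "will be added to all imputed values in the LY3303560 treatment groups prior to analyzing multiply imputed data".
- **How it is read.** The marginal mean of imputed measurements is said to be worse by delta "at each time point after discontinuation compared to the marginal mean of patients with observed data" at the same time point. The section also promises a judgement on whether the tipping point is clinically plausible.

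Delta runs over values "starting from 0 with increments of 0.10 until the null hypothesis can no longer be rejected". The section names neither the model nor the time point for the test on imputed data.

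Other sections show that a patient can lack an iADRS score while still on study. Under Section 6.3.2, if either component is missing, the "iADRS score will be considered missing". Section 6.16.2 plans a "Listing of patients missing site assessments and infusions because of COVID-19", separate from the listing of patients who discontinue for that reason. The per-protocol definition in Table 6.6.1 requires the primary endpoint at every scheduled visit, and Section 6.15 treats absent ADAS-Cog or ADL assessments as a significant violation.

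**The concern.** The first and last statements confine delta to the time after discontinuation. The two between them do not: every empty time point is imputed, and every imputed active-arm value is shifted. The closing interpretation is correct only if all imputed values fall after discontinuation, and nothing in the section ensures that.

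What is at stake is the meaning of the reported delta. A reader will take it as how much worse active-arm dropouts must have been to overturn the result, and will judge plausibility on that basis. Under the rule as written, delta also acts on missed ratings of patients who stayed in the study. A smaller shift may then suffice to tip the result, and the figure no longer answers the question the section asks.

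**Working it through.** The section states no numerical tipping point, so there is no plan figure to reproduce. The check has four parts.

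**1. Effect of scope on a Week 104 contrast, delta read as a worsening**

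Inputs from SAP Section 5.2:
- 360 enrolled at 1:1:1, so 120 per arm
- 30% dropout, so d = 0.30 and 120 × 0.70 = 84 per arm with data
- placebo decline 19.56 and 50% slowing on the high dose, so D = 0.50 × 19.56 = 9.78
- Week 104 standard deviation 20.9
- two-sided 0.05 (Section 6.1), so 1.96

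Assumed: m, the share of active-arm patients on study but without a Week 104 score. The SAP gives no such rate.

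SE = 20.9 × √(2/84) = 3.22. The high-dose mean must fall by D − 1.96 × SE = 9.78 − 6.32 = 3.46 points for significance to be lost. If a share f of active-arm values is shifted by delta, the mean falls by f × delta. Holding the SE fixed, the tipping point is 3.46/f. With discontinued patients only, f = d. With all imputed values, f = d + m.

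| Assumed m | Tipping point, 3.46/(0.30 + m) | Factor d/(d+m) | Smaller by |
|---|---|---|---|
| 0% | 11.5 | 1.00 | 0% |
| 1% | 11.2 | 0.97 | 3% |
| 2% | 10.8 | 0.94 | 6% |
| 5% | 9.9 | 0.86 | 14% |
| 10% | 8.6 | 0.75 | 25% |

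The point values depend on the planning effect, SD and sample size. The factor depends only on d and m.

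**2. Gaps only before Week 104**

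Such values do not enter a Week 104 mean, so f stays at d. A small multiple-imputation simulation agreed (8 visits, assumed correlation 0.9 between adjacent visits, 60 replicates). With 5% of on-study values missing at each earlier visit and none at Week 104, the ratio of the two tipping points was 1.00.

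**3. If the test averaged over visits**

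The same simulated data gave a ratio of about 0.8. The section does not name such an analysis. This only shows that the answer depends on a contrast left unspecified.

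**4. The sign as written**

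Section 6.3.2 builds iADRS from "1(ADAS - Cog_{13}) + 85] + ADCS-iADL", with a minus sign before the leading 1, so a higher score is better. Adding a non-negative delta raises active-arm scores. With the inputs above and f = 0.30, z = (9.78 + 0.30 × delta)/3.22:

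- delta 0: z = 3.03
- delta 5: z = 3.50
- delta 10: z = 3.96
- delta 20: z = 4.89

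The test moves away from the boundary and no tipping point is reached. Part 1 therefore applies only to delta read as a worsening, which is what the section intends.

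**The case against.** The best defence is context. The sentences before and after the operating rule both speak of the time after discontinuation, so all imputed values could be read within that scope. That makes the matter one of loose wording, but it does not settle it. The section expressly imputes every time point without a value and gives no rule for intermittent gaps, so a programmer following the text would shift them.

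A reader might go further and infer that on-study active-arm patients are certainly penalised, that the tipping point is certainly too small, and that a robust result will look fragile. The SAP does not support that, for these reasons:

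- Taken literally, the sign improves active-arm scores. The direction follows only from the stated intent.
- The Week 104 result moves only if patients still on study lack a Week 104 score, and nothing in the SAP says how many will. The COVID-19 listing belongs to the second interim analysis, timed to Week 52. Section 6.1.1 mentions phone and video visits and out-of-window visits, not scores lost at Week 104.
- Limited item-level gaps are already prorated under Section 6.3.2, so missing items alone will remove few scores.
- Shifting only the active arms is the declared design of this analysis, not a side effect of the wording.

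It is also fair to say that no claim or decision rule uses the tipping point.

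**Conclusion.** The mismatch between assumption and operation is real and can be seen within Section 6.11.3.4 alone. Read with delta as a worsening, applying it to on-study gaps can only leave the tipping point unchanged or make it smaller. At 30% dropout the reduction at Week 104 runs from 0% to 25% as m runs from 0% to 10%. Those rates are assumptions, and at the low end the effect is negligible.

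The point is minor. Under the intended sign the error is conservative, it is confined to an exploratory sensitivity analysis, and it leaves the primary disease progression model result untouched. It is still worth correcting, because the section promises to interpret delta clinically, and that is sound only if delta acts on the values it is said to describe. The sign in the same sentence is the more serious defect: correcting scope alone would leave an analysis that cannot tip.

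**What to change.** Replace the operating rule in Section 6.11.3.4 with text such as:

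> Delta is applied only to iADRS values imputed at scheduled visits after study discontinuation. iADRS scores missing at visits while the patient remains on study (after the proration rules of Section 6.3.2) are imputed under MAR without delta. Delta is applied in the worsening direction, that is, subtracted from the imputed iADRS value.

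It would help to name the contrast tested on the imputed data in the same edit, since the effect of the shift depends on it.

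The cost is a few sentences of SAP wording and a flag in the imputation program marking visits after discontinuation. No new data are needed: the time-to-discontinuation analysis in Section 6.7 already requires that date.

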#### **6.11.3.5. Bayesian Analysis of Shared Control**

Sensitivity of comparative inference for slowing the cognitive and/or functional decline of AD based on the shared control may be accomplished via Bayesian mixture modeling.

Supplementing the iADRS analyses with placebo data from studies I5T-MC-AACG, I8D-MC-AZES, and H8A-MC-LZAX will be explored and potentially based on matching baseline tau PET scan results (Viele, 2014).

#### **6.11.3.6. Slope Analyses**

Slopes of the iADRS will be assessed using an MMRM analysis. The change from baseline score at each post-baseline visit during the treatment period will be the dependent variable. The model will include the fixed, categorical effects of treatment, concomitant AChEI or memantine use at baseline (yes/no), pooled site, and continuous effects of baseline score, time, time-by-treatment interaction, and age at baseline. Time will be assumed to be a continuous variable calculated as number of days between baseline and each postbaseline visit (ie, [visit-baseline]+1) during the treatment period. The actual visit dates will be used to calculate number of days (time). The null hypothesis is that the contrasts of slopes of LY3303560 dose groups versus placebo equal zero.

A quadratic slopes model will also be fitted to these same scales. The quadratic model will include the linear component of time (TIME) and a quadratic component of time (TIME\*TIME), the linear component of time and treatment interaction (TIME\*TREATMENT) and quadratic component of time and treatment interaction (TIME\*TIME\*TREATMENT).

